### 11.1.7. Definitions Related to Safety

#### 11.1.7.1. Adverse Event

An *adverse event* (AE) is defined as any untoward medical occurrence in a clinical investigation subject that does not necessarily have causal relationship with treatment. An AE can therefore be any unfavorable and unintended sign (including clinically significant abnormal laboratory finding), symptom, or disease temporally associated with clinical study whether or not related to the investigational product.

Clinically significant findings or changes in assessments should be recorded as AEs. Every attempt should be made to describe the AE in the form of a diagnosis. If a clear diagnosis has been made, individual signs and symptoms will not be recorded unless they represent atypical or extreme manifestations of the diagnosis, in which case they should be reported as separate events. If a clear diagnosis cannot be established, each sign and symptom must be reported individually.

#### 11.1.7.2. Serious Adverse Event

AEs are classified as serious or non-serious. A *serious adverse event* is defined as any untoward medical occurrence that occurs during clinical study that meets one of the following criteria as shown in Table 6.

**Table 6: SAE Criteria and Definitions**

SAE Criteria	Definition
Death of Subject	An event that results in the death of the subject.
Life-Threatening	An event that, in the opinion of the Investigator, would have resulted in immediate fatality if medical intervention had not been taken. This does not include an event that would have been fatal if it had occurred in a more severe form.

SAE Criteria	Definition
Hospitalization	An event that results in an admission to the hospital for any length of time. This does not include an emergency room visit or admission to an out-patient facility.
Prolongation of Hospitalization	An event that occurs while the subject is hospitalized and prolongs the subject’s hospital stay.
Congenital Anomaly/Birth Defect	An anomaly detected at or after birth, or any anomaly that results in fetal loss.
Persistent or Significant Disability/Incapacity	An event that results in a condition that substantially interferes with the activities of daily living of a study subject. Disability is not intended to include transient interruptions of daily activities or experiences of relatively minor medical significance such as headache, nausea, vomiting, diarrhea, influenza, and accidental trauma (e.g., sprained ankle).
Important Medical Event Requiring Medical or Surgical Intervention to Prevent Serious Outcome 	An important medical event that, based on medical judgment, may not be immediately life-threatening or result in death or hospitalization, but may jeopardize the subject and may require medical or surgical intervention to prevent any of the outcomes listed above (i.e., death of a subject, life-threatening, subject hospitalization, prolongation of existing hospitalization, congenital anomaly, or persistent or significant disability/incapacity).

 Important Medical Events may be classified as serious or non-serious events at the discretion of the Investigator.

All AEs that do not meet the above criteria should be classified as ***non-serious adverse events***. Elective surgeries requiring hospitalization and hospitalizations for social reasons are not considered SAEs.

### 11.1.7.3. Adverse Event Follow-Up

Subjects with non-serious AEs that are ongoing at the subject’s last study visit must be followed until resolution or for 30 days after the subject’s last study visit, whichever comes first. Non-serious AE that are reported during the 7 days following the subject’s last study visit will be recorded on the Adverse Events CRF and followed until resolution or for up to the 30 days after the subject’s last study visit, whichever comes first. SAEs will be followed until the event resolves or the event or sequelae stabilize. SAEs that are reported within 30 days of the subject’s last study visit should be reported as indicated in [Section 11.1.10](#).

### 11.1.7.4. Adverse Event Reporting Period

AEs are to be recorded in the source documents from the time of the subject’s informed consent signature until the end of the subject’s study participation. Each AE, both serious and non-serious, will also be reported on the Adverse Events CRF. CRF Completion Instructions will be provided to each investigational site. If the subject reports or the Investigator learns of a new AE(s) up to 7 days after the subject’s last study visit or a new SAE(s) up to 30 days after the subject’s last study

visit, the investigational site personnel will ensure that these data are recorded on the Adverse Events CRF for the study. The period during which an SAE must be reported may be extended if there is a strong suspicion that the event being reported is related to the study medication or a study procedure.

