### 13.4.1. Adverse Events

Adverse events will be recorded throughout the study and at early discontinuation. Adverse events and medical conditions will be coded using the Medical Dictionary for Regulatory Activities (MedDRA) coding dictionary. Treatment-emergent adverse events will be defined as those events, which are newly occurring or worsening from baseline. In all cases only treatment emergent adverse events will be summarized.

Treatment-emergent adverse events will be summarized within each treatment group by primary system organ class (SOC) and preferred term. (**NOTE**: In any given category [e.g. body system] a subject will only be counted once.) The incidence rates of TEAEs will be analyzed as described in the SAP. Similar displays will be provided for SAE and prior (conditions ending prior to the first dose of study medication and current (conditions present while on study medication) medical conditions.

Adverse events will further be categorized by severity, relationship to study medication, and action taken. Other information collected will be listed, as appropriate. Any event starting more than 3 days after the final dose of study medication will be excluded from the above tables and only listed, unless the event caused discontinuation.

The proportions of subjects experiencing SAEs and AEs resulting in discontinuation from the study will be summarized by treatment groups.

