**20.2.3.4. COLE Visit 2-Visit 6 (Day 28, Day 84, Day 140, Day 196, Day 280 ± 5 days)**

On COLE Visit 2, COLE Visit 3, COLE Visit 4, COLE Visit 5 and COLE Visit 6, patients will return to the site to be queried for any adverse events and updates to their current medication use. Patients will undergo a physical examination (PE), vital signs, ECG, C-SSRS, urine drug screen, urine and serum pregnancy test, if applicable, and clinical laboratory results. Patients will complete the since last visit C-SSRS, Modified Gastroparesis Cardinal Symptom Index (mGCSI), Modified Pagi-SYM (mPagi-SYM), Clinical Global Impression of Severity (CGI-S), Patient Assessment of Upper Gastrointestinal Disorder Quality of Life (Pagi-QOL). Daily diary compliance will be reviewed, study medication will be collected and reviewed, and new study drug will be dispensed.

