### 20.2.4.2. Early Withdrawal of Subjects

The term “discontinuation” refers to the subject’s premature withdrawal from the study before completing all scheduled evaluations.

Subjects may voluntarily withdraw from the COLE at any time for any reason. Subjects may also be discontinued from the study for any of the following reasons:

- If in the Investigator’s judgment, continuation in the study may prove harmful to the subject. Such a decision may be precipitated by adverse events, including changes in vital signs, physical examination, ECG, or laboratory tests. The Investigator will maintain autonomy in making medical/safety decisions regarding the subject’s continued participation in the trial. Clinically notable abnormalities in vital signs or laboratory tests are provided in [Appendices 20.4](#) and [20.3](#), respectively, to guide clinical focus regarding a subject’s continued participation;
- Noncompliance;

For subjects withdrawing from the study prematurely, all efforts will be made to perform the COLE Visit 7 Early Termination procedures.

Documented reason:

It will be documented whether or not each subject completed the clinical study. If, for any subject, study treatment or observations were discontinued, the reason will be recorded (only 1 choice is acceptable) on the electronic case report form (electronic CRF). Acceptable reasons for a subject discontinuing participation in this clinical study are as follows:

9. Protocol deviation (including noncompliance to study requirements)
10. Adverse event(s) (including abnormal laboratory values, and abnormal test procedures)
11. Pregnancy
12. Lost to follow-up
13. Death
14. Subject withdrew consent
15. Unsatisfactory therapeutic effect
16. Other (specify).

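### Post-study AE and SAE windows run from the last visit, so a subject who stops between visits and does not return has little or no off-drug collection, mainly for SAEs in the COLE

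*Combined protocol and SAP*

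**What the plan says.** Section 11.1.7.4 gives two rules. The general rule is that AEs are recorded "from the time of the subject’s informed consent signature until the end of the subject’s study participation". The legible text does not define that end for a subject who stops without a visit. The second rule covers what the site hears of afterwards: any "new AE(s) up to 7 days after the subject’s last study visit or a new SAE(s) up to 30 days after" that visit goes on the AE form. Section 11.1.7.3 has the same anchor: "SAEs that are reported within 30 days of the subject’s last study visit should be reported as indicated in" Section 11.1.10. Section 11.1.7.4 adds some discretion for suspected relatedness: "The period during which an SAE must be reported may be extended if there is a strong suspicion" of a link to the study drug or a procedure.

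The analysis uses a different anchor. In Section 13.4.1, "Any event starting more than 3 days after the final dose of study medication will be excluded from the above tables" and is only listed, unless it led to discontinuation.

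Drug is dispensed to cover the time to the next visit (Sections 8.2, 20.1.8 and 20.2.8). COLE Visits 2 to 6 fall on "Day 28, Day 84, Day 140, Day 196, Day 280 ± 5 days". The termination visit after early withdrawal is an aim and not a certainty: "all efforts will be made to perform the COLE Visit 7 Early Termination procedures" (Section 20.2.4.2; Section 6.3 has the same wording for Visit 4).

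**The concern.** A window counted from the last visit works as an off-drug window only when that visit falls at about the last dose. Subjects who attend a final or termination visit at that time are unaffected. A subject who goes on dosing from a take-home supply, then stops and does not come back, has used up part or all of the 7 or 30 days while still on drug.

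What is at stake is the record of new events soon after stopping. Section 11.1.8 judges causality partly on response to withdrawal of the drug, so off-drug information has a use. Long-term safety is the primary objective of the COLE (Section 20.2.1.1), and the COLE has the longest visit gaps. Adverse events and loss to follow-up are both listed discontinuation reasons, so non-returners may plausibly include people who stopped for a safety reason.

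**Working it through.** The plan states no figure on this point, so the check is date arithmetic.

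**Inputs**
- Windows W, counted from the last study visit: 7 days (AE) and 30 days (SAE), Sections 11.1.7.3 and 11.1.7.4.
- Visit days: double-blind 0, 14, 28 (Section 9.1); OLE to 56 and 84 (Section 20.1.10); COLE 0, 28, 84, 140, 196, 280, 364 (Sections 20.2.3.4 and 20.2.3.6; Section 20.2.11.3 gives 365 for the last, a one-day difference).
- D: days from the last attended visit to the next scheduled one, taken as the days of dosing that the dispensed supply allows.

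**Window against supply.** Shortfall = D − W. A positive value means that the window closes before the supply runs out. A negative value means that it closes after.

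| Interval | D | AE: D − 7 | SAE: D − 30 |
|---|---|---|---|
| Double-blind | 14 | 7 | −16 |
| OLE | 28 | 21 | −2 |
| COLE Visit 1 to 2 | 28 | 21 | −2 |
| COLE Visit 2 to 3, 3 to 4, 4 to 5 | 56 | 49 | 26 |
| COLE Visit 5 to 6, 6 to 7 | 84 | 77 | 54 |

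**Sensitivity to spare capsules.** A bottle of 36 capsules at 2 per day lasts 18 days (Section 8.2).
- Double-blind, one bottle: AE 18 − 7 = 11; SAE 18 − 30 = −12.
- OLE, assuming two bottles (36 days): AE 29; SAE 6. The SAE window therefore outlasts dosing in the OLE only on the nominal schedule.
- COLE packaging text is redacted. Assuming the same bottle, 56 days need 112 capsules, so 4 bottles or 72 days (SAE 42). Likewise 84 days need 168 capsules, so 5 bottles or 90 days (SAE 60).

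**Off-drug cover.** If the last dose falls t days after the last attended visit and no further visit takes place, the off-drug SAE window is max(0, 30 − t) days and the AE window max(0, 7 − t) days. A double-blind subject dosing to the end of an interval keeps 30 − 14 = 16 days for SAEs. SAE cover is zero for any stop more than 30 days after the visit, which on nominal intervals can happen only in the COLE. As an illustration, assume stopping times spread evenly over the gap (the documents give no distribution). Mean SAE cover among non-returners is then (30 × 30 / 2)/56 = 8.0 days or 450/84 = 5.4 days. It is nil for 26/56 = 46% or 54/84 = 64% of stopping times.

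**Example.** A subject is last seen on COLE Day 280, takes the last dose on Day 336, withdraws at that day's call and attends no termination visit. The SAE window closed on 280 + 30 = Day 310, which is 336 − 310 = 26 days before the last dose. If participation ends on Day 336, events up to then are recorded. Section 13.4.1 tabulates events starting up to 336 + 3 = Day 339. An SAE on Day 338 would belong in the displays but lies outside both collection rules. An SAE on Day 340 would be listed only, even with a dose-based window, unless it caused discontinuation.

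**The case against.** The case on the other side is substantial.

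- **Recording runs to the end of participation.** A reader might infer that collection closes while the subject is still dosing. The documents do not support that: a subject dosing under the protocol is naturally read as still participating. This stands, and it confines the point to the off-drug period.
- **The displays end 3 days after the final dose.** A reader might infer that tabulated SAE counts are biased low by up to 30 days of events. Section 13.4.1 rules that out. Only events within 3 days of the final dose, or events that caused discontinuation, can be missing from the displays. The rest of the loss is in listings and SAE reporting.
- **COLE calls ask about AEs about every 4 weeks.** The 54-day figure needs a subject who takes the whole 84-day supply and, after Day 280, is not reached at Day 308 or Day 336. If a call counted as a visit, the SAE gap would vanish. However, Section 20.2.3.1 lists calls apart from visits, and Section 20.2.3.5 provides for an unscheduled visit if a call warrants one. Calls limit the loss while contact lasts and give no cover after withdrawal.
- **Other safeguards exist.** The extension clause is discretionary and needs suspicion first. Section 6.3 follows subjects who discontinue for an AE for up to 30 days, but that covers the triggering event and not new ones.
- **Section 11.1.9.2 is redacted.** The contents list it as dealing with post-study adverse events. One therefore cannot say that the extension clause is the only recourse, or that off-drug SAEs are never required.
- **The window is passive.** Sites record what they learn, and moving the anchor does not create contact. This stands. The gain is that an event the site does hear of falls inside the stated period.

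**Conclusion.** The point holds as a defect in the anchor, with a limited reach. A subject who stops between visits and attends no termination visit has a shortened off-drug collection period, or none. For SAEs the effect is mainly in the COLE, where the window can end up to 26 days (56-day gap) or 54 days (84-day gap) before the supply would run out on nominal intervals. In the double-blind phase the SAE window outlasts planned dosing by 16 days, and nominally in the OLE by 2. The AE window falls short there by 7 and 21 days.

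A reader might also infer that safety capture differs between the randomized arms. The documents give no ground for that: it would need different non-return rates by arm, and in that phase only the AE window ends before planned dosing does.

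The conclusion assumes that calls are not visits, that supply matches the visit interval, and that the redacted Section 11.1.9.2 does not already set a dose-based rule. If it does, it conflicts with Sections 11.1.7.3 and 11.1.7.4, and the passages must be reconciled. The share of subjects affected is unknown and may be small.

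**What to change.** In Sections 11.1.7.3 and 11.1.7.4, count the 7-day and 30-day periods from the last dose of study medication or the last study visit, whichever is later. When the subject does not return, use the last dose date that the subject reports. Failing that, use the last date that the dispensed supply could cover. Sections 20.1.12 and 20.2.13 refer back to Section 11, so the OLE and COLE follow. Check Section 11.1.9.2 against the new wording.

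Every subject then has 7 days (AE) and 30 days (SAE) of off-drug collection by construction, and the 3-day cut-off in Section 13.4.1 falls inside what is collected. The cost is two sentences in an amendment, an update to the CRF completion instructions, and a slightly longer collection period for subjects who do not return. No visit, procedure or sample-size figure changes.

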#### **11.1.7.5. Pre-Existing Condition**

A pre-existing condition is one that is present at the start of the study. A pre-existing condition should be recorded as an adverse event if the frequency, intensity, or the characteristics of the condition worsen during the study period.

#### **11.1.8. Relationship to Study Medication**

Each AE is to be reported on the AE CRF. The Investigator is responsible for making an assessment of the likelihood that an AE is causally related to the study medication. The Investigator should choose one of the five choices of causality.

- **Certain:** occurs in a reasonable time after study drug administration and cannot be explained by concurrent disease or drugs. The event should respond to withdrawal of study drug (de-challenge) and recur with re-challenge when clinically plausible.
- **Probable:** occurs in a reasonable time after study drug administration and it is unlikely to be attributed to concurrent disease or drugs, and it has a response to de-challenge. Re-challenge information is not required to fulfill this definition.
- **Possible:** occurs in a reasonable time after study drug administration, but could be related to concurrent disease or drugs. De-challenge information may be lacking or unclear.
- **Unrelated:** the event has an improbable temporal relationship (too soon, or too late after study drug, or study drug is not taken) and is plausibly related to other drugs or underlying disease.
- **Unassessable:** available information is insufficient, contradictory, and cannot be supplemented or verified at the time of the report. **This assessment will be considered as “related” for all expedited reports until an alternative assessment is made.**

Adverse Event causality of “certain”, “probable”, “possible”, and “unassessable” will be considered related to study medication.

#### **11.1.9. Recording Adverse Events**

##### **11.1.9.1. Adverse Events During Study Period**

At each study visit, the Investigator must seek information on AEs by questioning the subject and, as appropriate, by examining the subject. Information on all AEs should be recorded immediately in the source document, and also in the appropriate AE module of the CRF. All

signs, symptoms, and abnormal diagnostic procedure results that are considered clearly related should be grouped and recorded in the source document as one diagnosis. All AEs occurring during the study period must be recorded.

[REDACTED]

[REDACTED]

**11.1.10. Reporting Adverse Events**

**11.1.10.1. Study Sponsor Notification by Investigator**

All SAEs should be reported on the electronic CRF within 24 hours to the Vanda Drug Safety designee using the AE electronic CRF page.

[REDACTED]

[REDACTED]

[REDACTED] Table 7 [REDACTED]

[REDACTED]

[REDACTED] [REDACTED] [REDACTED]	[REDACTED] [REDACTED] [REDACTED]
--	--

[REDACTED]

[REDACTED]  
[REDACTED]  
[REDACTED]

[REDACTED]

[REDACTED]  
[REDACTED]

[REDACTED]  
[REDACTED]  
[REDACTED]  
[REDACTED]

## 12. PHARMACOGENOMICS ASSESSMENT

The pharmacogenomic assessment is an exploratory assessment. [REDACTED]

[REDACTED]

[REDACTED]

[REDACTED]

[REDACTED]

[REDACTED]

## **13. STATISTICS**

### **13.1. Sample Size and Accrual**

Based on a two-sided t-test with the 5% significance level, the planned sample size of 75 subjects per arm (a total of 150 subjects) provides around 86% power to detect a mean difference of 0.8 point in the average of nausea severity score assuming the standard deviation of 1.6 in each treatment group.

### **13.2. Statistical Methods and Analysis Plan**

This section describes the planned statistical analyses in general terms. A complete description of the methodology will be specified in a statistical analysis plan (SAP). Any changes in the statistical methods described in this protocol that occur prior to database lock will be documented in the SAP and will not require a protocol amendment.

#### **13.2.1. General**

Statistical analyses will be performed using two-sided tests.

Data will be summarized by treatment group (and by visit when applicable), with respect to demographic and baseline characteristics, efficacy variables, and safety variables.

Summary statistics will include the mean, N, standard deviation, median, minimum, and maximum values for continuous variables, and frequencies and percentages for categorical variables.

Continuous efficacy variables will be analyzed using a mixed-effect model for repeated measures (MMRM) and/or an analysis of covariance (ANCOVA) model. The models will be described in the SAP.

For the analyses of change from baseline, only subjects with a baseline and at least one (1) post-baseline measure will be included in the analysis. Unless otherwise specified, baseline is defined as the latest non-missing observation across all the visits in the screening phase, before the active study drug begins. Endpoint will be the latest non-missing observation across all the post-baseline visits in the evaluation phase.

Low enrolling sites will be pooled for analysis and the pooling algorithm will be determined prior to breaking the blind. The goal of pooling low enrolling sites is to have a sufficient number of subjects per treatment group within a site for the analysis models and for the evaluation of the

treatment-by-site interaction for the primary endpoint. Unless otherwise specified, the pooled sites will only be used in the analyses where site is included. The actual sites rather than the pooled sites will be specified in data listings.

Categorical variables will be analyzed using the Cochran-Mantel-Haenszel (CMH) test blocking on sites, and Fisher's exact test will be used when site is not adjusted (mainly for safety assessment).

Details of the model and the analyses will be specified in the SAP. All statistical analyses will be performed using SAS®, Version 9.1.3 or higher.

